# 7.1.3 Other Risks for MRI

All MRI studies performed under this protocol will not exceed the FDA guidelines for magnetic resonance in any way. As in the circumstances of all MRI scanning, the single greatest risk of MRI for subjects is the possibility of a ferromagnetic object flying towards the magnet and hitting the subject while the subject is in the scan room. Depending on the object size and shape, the potential for harm could be great. In order to assure against such an event, all persons present at the study (subject, investigators, technicians, etc.) are screened for metal objects which are removed and placed in a safe location away from the magnet room. In the event an accident or incident of any kind should occur while the subject is in the MRI Center or the magnet, all investigators and associated staff are trained in calling codes and performing CPR. Emergency procedures have been established and a manual containing these procedures is kept in the console room.

MRI machines are long narrow, cylindrical tubes which can cause a feeling of claustrophobia or panic in some patients. If patients suffer from claustrophobia, they will be excluded from the study. The technologist performing the scan will have voice contact with the subject while they are in the MRI scanner. If the subject feels the need to be removed from the MRI scanner at any time, then the scan will be stopped immediately.

# 7.1.4 Adverse Event Characteristics

• CTCAE term (AE description) and grade: The descriptions and grading scales found

in the revised NCI Common Terminology Criteria for Adverse Events (CTCAE) version 4.0 will be utilized for AE reporting. All appropriate treatment areas should have access to a copy of the CTCAE version 4.0. A copy of the CTCAE version 4.0 can be downloaded from the CTEP web site http://ctep.cancer.gov/protocolDevelopment /electronic applications/etc.htm.

### • For expedited reporting purposes only:

AEs for the agent(s) that are listed above should be reported only if the adverse event varies in nature, intensity or frequency from the expected toxicity information which is provided.

Other AEs for the protocol that do not require expedited reporting are outlined in the next section (Expedited Adverse Event Reporting) under the sub-heading of Protocol-Specific Expedited Adverse Event Reporting Exclusions.

### • **Attribution** of the AE:

Definite - The AE *is clearly related* to the study treatment. Probable - The AE *is likely related* to the study treatment. Possible - The AE *may be related* to the study treatment. Unlikely - The AE *is doubifully related* to the study treatment. Unrelated - The AE *is clearly NOT related* to the study treatment.

### 7.1.5 Expedited Adverse Event Reporting

Investigators **must** report to the Overall PI any serious adverse event (SAE) that occurs after the initial dose of study treatment, during treatment, or within 30 days of the last dose of treatment on the local institutional SAE form.

### 7.1.6 DF/HCC Expedited Reporting Guidelines

Investigative sites within DF/HCC will report AEs directly to the DFCI Office for Human Research Studies (OHRS) per the DFCI IRB reporting policy.

	OF/HCC Reportable AEs					
Attribution	Gr. 2 & 3 AE Expected	Gr. 2 & 3AE Unexpected	Gr. 4AE Expected	Gr.4AE Unexpected	Gr. 5 AE Expected or Unexpected	
Unrelated Unlikely	Not required	Not required	5 calendar days#	5 calendar days	24 hours*	
Possible Probable Definite	Not required	5 calendar days	5 calendar days#	5 calendar days	24 hours*	
# If listed in protocol as expected and not requiring expedited reporting, event does not need to be reported.						

\* For participants enrolled and actively participating in the study *or* for AEs occurring within

30 days of the last intervention, the AE should be reported within  $\underline{1 \text{ business day}}$  of learning of the event.

### 7.1.7 Expedited Reporting to Hospital Risk Management

Participating investigators will report to their local Risk Management office any participant safety reports or sentinel events that require reporting according to institutional policy.

7.1.8 Routine Adverse Event Reporting

All Adverse Events **must** be reported in routine study data submissions to the Overall PI on the toxicity case report forms. **AEs reported through expedited processes (e.g., reported to the IRB, FDA, etc.) must** also be reported in routine study data submissions.

### 7.2 Reader Study

There are no expected AE related to the reader study.

### 8. IMAGING AGENT INFORMATION

A list of the adverse events and potential risks associated with the investigational or other agents administered in this study can be found in Section 7.1.

### 9. STUDY CALENDAR

#### 9.1 **Prospective Patient Recruitment, Year 1**

	Visit la,b
	Screening
	&exam
Informed Consent	Х
Medical History	Х
Urine pregnancy	Xe
Test	AC
Blood Test	Xct
Contrast	Xe
Mammogram	ле
Breast MRI	Xe

Patient Experience Survey	Xr
Breast Biopsy	Х

a If abnormal findings are detected on the contrast mammogram or breast MRI, there is the potential that additional standard of care tests and procedures will need to be performed. These may occur on the same day or at a later date.

b The contrast mammogram and the breast MRI may be performed on the same day or on different days. They may also be performed on the same day or a separate day from the breast biopsy.c For patients who are of child-bearing potential, and having both MRI and CESM performed on the same day, they will receive a single pregnancy test immediately before the imaging tests are performed. If the studies are not performed on the same day, then they will have a pregnancy test before each of the imaging tests on the day of the imaging exams. et For patients having both MRI and CESM performed on the same day, they may need to get blood work testing how their kidneys work. This will happen once immediately before the imaging tests, on the day of the imaging exams. If the MRI and CESM are performed on different days, they may need blood work before each imaging test.e If either the contrast mammogram or the breast MRI are performed as part of standard of care, then they will be billed to insurance. If they are performed for research purposes only, then they will be billed to the grant. fThe patient experience survey will only be given once after the second of the two imaging tests has been performed.

	Months 0- 12	Month 13- 15	Month 16	Months 17-19	Months 20- 22	Months 23-24
Prospective Image acquisition	Xxx					
Image Categorization		Xxx				
Training Session			xxx			
Reader Study - session I				xxx		
Reader Study - session 2					xxx	
Data analysis						xxx
Report						xxx

# 9.2 Reader Study, Year 2

# **10. MEASUREMENT OF EFFECT**

### 10.1 Reader Study

Each reader will interpret 150 CESM and 150 MRI cases in two sessions, separated by a one month washout period. Each reader will independently review and score each of the image sets of the Reader Study Case Set. The method for interpretation is below:

## A. CESM session:

--+ Review and score the low energy images (these images are equal to conventional 2D mammographic images); this will be the MG score

--+ Then review and score the low energy images combined with the subtraction images (this is the CESM exam); this will be the CESM score.

### B. MRI session:

--+ Review and score the abbreviated MRI sequences (these are a subset of the full protocol); this will be the abMRI score. --+ Then review and score the complete MRI exam; this will be the MRI score.

The order of image presentation per reader is randomized. Half will complete the CESM session first and the other half will complete the MRI session first. Cases will be randomized and counterbalanced to account for learning, experience, and fatigue that occur during reader studies. Readers and study assistants will be blinded to the details of the investigational site, subject history, previous mammography images, and previous clinical results. The radiologists will score each case with a BIRADS (Breast Imaging Reporting and Data System) score of 1,2,3,4a, 4b, 4c, or 5 defined, respectively, as negative, benign findings, probably benign findings, low suspicion for malignancy, moderate suspicion for malignancy, high suspicion for malignancy and highly suggestive of malignancy associated with probability of malignancy of (0%), (0%), (:S2%), (>2% to :S10%), (>10% to :S50%), (>50% to <95%), and (2:95%), respectively. Each case will also be scored for confidence in diagnosis on a 5-point Likert scale using strongly confident, confident, neutral, not confident, and strongly not confident. This will be the *confidence score*. Readers will report their interpretations into RedCap database using reader ID numbers and the results will be analyzed anonymously.

# **10.2** Other Response Parameters

Information on patient preferences of CESM versus MRI will be recorded using a survey in RedCap

# **11. DATA REPORTING / REGULATORY REQUIREMENTS**

Adverse event lists, guidelines, and instructions for AE reporting can be found in Section 7.0 (Adverse Events: List and Reporting Requirements).

# **11.1 Prospective Patient Recruitment**

11.1.1 Data Reporting

Patients will be registered in the Oncore system. Study patient data will be captured in an institutional RedCap system designed and maintained by the study team.

**11.1.2** Data Safety Monitoring

The DF/HCC Data and Safety Monitoring Committee (DSMC) will review and monitor toxicity and accrual data from this study. The committee is composed of clinical specialists with experience in oncology and who have no direct relationship with the study. Information that raises any questions about participant safety will be addressed with the Overall PI and study team.

The DSMC will review each protocol up to four times a year or more often if required to review toxicity and accrual data. Information to be provided to the committee may include: up-to-date participant accrual; current dose level information; DLT information; all grade 2 or higher unexpected adverse events that have been reported; summary of all deaths occurring with 30 days of intervention for Phase I or II protocols; for gene therapy protocols, summary of all deaths while being treated and during active follow-up; any response information; audit results, and a summary provided by the study team. Other information (e.g. scans, laboratory values) will be provided upon request.

# 11.2 Reader Study

Data reporting will be entered into an institutional RedCap system designed and maintained by the study team

# 11.3 Multicenter Guidelines

NIA

# 11.4 Collaborative Agreements Language

NIA

# **12. STATISTICAL CONSIDERATIONS**

This is a retrospective reader study to compare screening MRI and contrast enhanced spectral mammography for breast cancer screening, for which some cases will be prospectively collected.

# 12.1 Study Design/Endpoints

Exams will be interpreted by 13 radiologist readers. Each reader will score each CESM and MRI exam according to the Breast Imaging-Reporting and Data System (BI-RADS), ranging from 1-5. The score used will correspond to the most suspicious finding in the study. The primary outcome will be whether the exam is benign or malignant. BI-RADS scores 1, 2, and 3 associated with the corresponding categories of negative, benign findings, and probably benign findings will be negative (benign). BI-RADS scores 4 and 5 associated with the corresponding categories of suspicious for malignancy will be positive (malignant).

Positive truth will be determined by histopathology confirming malignant pathology. If a woman has had both a percutaneous breast biopsy and surgical excision, the worst pathology will be considered for analysis.

Negative truth will be considered for all cases categorized as negative or biopsy proven benign. All cases will require two-year follow-up to confirm the absence of malignancy. The follow-up will take the form of any documentation of the woman's health to include the online medical record (OMR) or imaging archival system, or direct communication with her.

At the time of the reader study, there may be cases classified as negative that have not had complete follow-up since their initial CESM and MRI exams. These cases will be reevaluated after the reader study has been completed to confirm whether the cases represent false negatives. This will be accounted for in the subsequent analysis. Given that the false negative rate of MRI is low and approximates 3%, it is unlikely that this will impact the analysis significantly (17).

We will compare the BI-RADS score of CESM and MRI with the final outcome of negative or positive truth to determine the area under the curve for each technology for ROC analysis.

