A. CESM session: - Review and score the low energy images (these images are equal to conventional 2D mammographic images); this will be the MG score

- Then review and score the low energy images combined with the subtraction images (this is the CESM exam); this will be the CESM score.

B. MRI session: - Review and score the abbreviated MRI sequences (these are a subset of the full protocol); this will be the abMRI score. - Then review and score the complete MRI exam; this will be the MRI score.

The order of image presentation per reader is randomized. Half will complete the CESM session first and the other half will complete the MRI session first. Cases will be randomized and counterbalanced to account for learning, experience, and fatigue that occur during reader studies. Readers and study assistants will be blinded to the details of the investigational site, subject history, previous mammography images, and previous clinical results. The radiologist reader will provide a forced BIRADS score of 1,2,3,4a, 4b, 4c, or 5 defined, respectively, as negative, benign findings, probably benign findings, low suspicion for malignancy, moderate suspicion for malignancy, high suspicion for malignancy, and highly suggestive of malignancy associated with probability of malignancy of (0%), (0%), (::=::2%), (>2% to ::=;10%), (>10% to ::=;50%), (>50% to <95%), and (95%), respectively. Each case will also be scored for confidence in diagnosis on a 5-point Likert scale using strongly confident, confident, neutral, not confident, and strongly not confident. This will be the confidence score. Readers will report their interpretations into RedCap database using reader ID numbers and the results will be analyzed anonymously.

The reader study will take place after all the imaging studies have been acquired and reported. Consensus will not be necessary for the reader study. We will be evaluating individual and group ROC curves.

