# 2. BACKGROUND

### 2.1 Study Disease(s)

The limitations of conventional mammography, with its inability to detect breast cancers in dense breast tissue and subsequent reduced sensitivity, are now well-established and have resulted in new legislation in nearly 50% of US states requiring reporting breast tissue density to patients and recommending supplemental imaging screening with ultrasound and MRI. The decreased sensitivity is especially concerning in the intermediate and high-risk groups (6-11). MRI has become the prime alternative in these groups but has its own limitations including increased false positives associated with unnecessary biopsies and anxiety, increased cost, increased time, and decreased availability at many centers (12). Ultrasound is another, less commonly used alternative as it is associated with even more false positives than MRI, is time intensive, and operator dependent.

CESM is a new imaging tool using a dual-energy technique that has been shown in the diagnostic setting to have increased sensitivity for breast cancer detection relative to conventional 2D imaging and equal sensitivity with improved specificity relative to breast MRI. It was FDA approved for diagnostic imaging in 2011. It requires no additional time relative to conventional 2D imaging other than IV line placement and contrast administration and is overall faster than breast MRI. It is less expensive than breast MRI as it is currently being billed as a diagnostic mammogram and is easier to implement into practice than MRI given that it is simply a software upgrade to commonly used mammography equipment and the staff training is minimal.

Given these benefits, CESM may prove to be useful in the screening setting, where traditional imaging tools including 2D imaging, MRI, and ultrasound have shortcomings. This is especially important for those patients who cannot get the more traditional imaging. However, CESM's value in screening has not yet been established. This will be the first reader study that evaluates CESM's role for screening relative to 2D mammography and MRI.

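### Exam-level scoring with no recorded location means the primary AUC measures case-level accuracy and cannot be read as detection of the cancer itself

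*Combined protocol and SAP*

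**What the plan says.** Section 12.1 sets the scoring unit: "The score used will correspond to the most suspicious finding in the study". BI-RADS 4 and 5 count as positive. Truth is also set per case: "Positive truth will be determined by histopathology confirming malignant pathology". The two are joined at that level: "We will compare the BI-RADS score of CESM and MRI with the final outcome of negative or positive truth".

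Section 1.1.4, repeated in substance in section 10.1, lists what a reader records. There are two items: "The radiologist reader will provide a forced BIRADS score of 1,2,3,4a, 4b, 4c, or 5" and "Each case will also be scored for confidence in diagnosis on a 5-point Likert scale". No section asks for side, quadrant or a mark, or for the scored finding to be matched to the proven cancer.

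Readers search without help: "Readers and study assistants will be blinded to the details of the investigational site, subject history, previous mammography images, and previous clinical results". Section 3.2.1 requires CESM views of both breasts.

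Section 12.2 frames Objective 1 as accuracy for detecting breast cancer. It sets the hypotheses and the -0.05 margin on the difference in reader-average AUC.

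**The concern.** Suppose a reader misses the biopsied cancer and gives BI-RADS 4 to an unrelated benign area. Under section 12.1 that read is a true positive, as if the cancer had been found. Such reads are plausible here. Readers search both breasts without history or prior images, and section 1.1.2 spreads recruitment evenly over BI-RADS 4A to 5 so that subtle cancers are included.

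What is at stake is the meaning of the result. Objective 1 speaks of detecting cancer, while the analysed quantity mixes finding the cancer with calling something else in a woman who has cancer. If CESM finds fewer cancers than MRI, wrong-site credit hides part of that deficit. The reader record as described would not allow the two kinds of positive call to be separated afterwards.

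**Working it through.** **Plan's own figure.** The documents give no wrong-site rate and no location-matched target, so there is no figure on this point to reproduce. Every rate below is an assumption.

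**1. Sensitivity at the BI-RADS 4 threshold.** Let s be the probability that a reader calls the proven cancer at its true site. Let f be the probability of a positive call elsewhere, given that the true site was not called.

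Case sensitivity = s + (1 - s)f

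With the same f in both modalities, the apparent gap is (1 - f) x (true gap).

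**2. AUC scale.** The margin is on AUC. With one threshold, AUC = (sensitivity + specificity)/2. If specificity is equal, it cancels and the AUC gap is half the sensitivity gap. Assume correct-site sensitivity of 0.90 (MRI) and 0.80 (CESM), a true gap of 0.10, or 0.05 in AUC:

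| Assumed f | MRI | CESM | Sensitivity gap | AUC gap |
|---|---|---|---|---|
| 0 | 0.900 | 0.800 | 0.100 | 0.050 |
| 0.02 | 0.902 | 0.804 | 0.098 | 0.049 |
| 0.05 | 0.905 | 0.810 | 0.095 | 0.0475 |
| 0.10 | 0.910 | 0.820 | 0.090 | 0.045 |
| 0.20 | 0.920 | 0.840 | 0.080 | 0.040 |
| 0.30 | 0.930 | 0.860 | 0.070 | 0.035 |

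For f = 0.30: 0.90 + 0.10 x 0.30 = 0.93 and 0.80 + 0.20 x 0.30 = 0.86.

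**3. Direction.** The factor works both ways. With equal sensitivities there is no gap to shrink. If CESM were the better modality by 0.10, f = 0.30 would show an advantage of only 0.07.

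**4. Cross-check over the whole ROC curve.** On a cancer case, let the exam score be the larger of a lesion score L and an elsewhere score N. On a non-cancer case it is an elsewhere score N'. Let A be the probability that L exceeds both N and N'. If N and N' behave alike, each is the largest of the three with probability (1 - A)/2, so

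Case AUC = A + (1 - A)/2 = (1 + A)/2

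Differences in A are then halved. The AUC of 0.83 assumed in section 12.2 gives A = 2 x 0.83 - 1 = 0.66, and solving the model numerically puts the top finding off-site in 22% of cancers. That is an upper scenario, in which every cancer case has a competing finding. With fewer competing findings, a true CESM deficit of -0.08 in A appears as follows:

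| Top finding off-site (share of all cancers) | Apparent AUC difference |
|---|---|
| 0% | -0.080 |
| 1.7% | -0.075 |
| 4.5% | -0.068 |
| 9.5% | -0.057 |
| 15.3% | -0.048 |
| 22% | -0.040 |

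This share is of all cancers, whereas f is conditional on a miss, so rows of the two tables should not be compared.

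**5. Standard error, for scale only.** The components in section 12.2, with a case variance of 0.00170 (Hanley-McNeil at AUC 0.83, 44 and 88 cases), give 2/13 x [0.002 x (1 - 0.8) + 0.0004 + 0.00170 x (0.53 + 12 x 0.04)] = 0.000387, so SE = 0.0197. The SE implied by the stated 80% power (normal approximation, no true difference) is about 0.0178. The discrepancy is a separate matter, and nothing in steps 1 to 4 depends on it.

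**The case against.** **The test is sound for what it tests.** Section 12.1 defines the outcome as the benign or malignant status of the exam, and section 12.2 sets the hypotheses, margin and assumed AUC at case level. The error rate holds for that quantity. This stands, and it limits the point to interpretation.

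**A reader might infer that false non-inferiority verdicts are inflated.** With the standard errors in step 5, an AUC gap of 0.05 that appears as 0.035 would pass in about 12% to 13% of trials: (0.05 - 0.035)/0.0197 - 1.96 = -1.20 and (0.05 - 0.035)/0.0178 - 1.96 = -1.12. Under the halving in step 4 the figure is 25% to 29%. Neither is an error rate of this plan. Both apply -0.05 to a location-matched quantity for which the plan sets no margin.

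**A reader might also infer that extra MRI false positives tilt the result towards non-inferiority,** because section 2.1 says that MRI "has its own limitations including increased false positives associated with unnecessary biopsies and anxiety". The documents do not support this. Wrong-site credit to MRI on cancer cases raises MRI's AUC, which works against CESM. The same tendency on the 88 non-cancer cases lowers MRI's AUC. In the step 4 model, changing the spread of MRI elsewhere scores (SD 0.8 to 1.5) at equal A left the AUC difference at 0. A shift needs off-site suspicion on MRI cancer cases beyond that on non-cancers; 0.25 SD of it moves the difference by about -0.03, against CESM. The documents give no data on this.

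**CESM may not be worse.** Section 2.1 reports equal sensitivity and better specificity than MRI in the diagnostic setting. On that premise a common f has no sensitivity gap to act on. This stands as a premise, but the trial exists to test it.

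**The REDCap form is not reproduced,** so it may already hold a location field. That is possible. The protocol would still lack any use for it.

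**Conclusion.** The omission is real: as described, a wrong-site call on a cancer case counts as a detection and cannot be told apart from a correct one. The consequence is a limit on interpretation. Case-level AUC remains a valid primary endpoint, but a non-inferior result would not show that CESM finds the cancer as often as MRI does.

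The size depends on an unknown rate. Under a common f and equal specificity, true gaps shrink by (1 - f): a 0.05 single-threshold AUC gap appears as 0.035 at f = 0.30 and as 0.049 at f = 0.02. In the full-curve model, a location-matched deficit of -0.08 appears inside -0.05 only when the top finding is off-site in about 15% of cancers or more. The shrinkage is symmetric and helps a non-inferiority verdict only if CESM is truly worse. The documents do not support a general claim that the scoring rule favours non-inferiority.

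The change is worth making because it is cheap and the information must be captured at reading time.

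**What to change.** Keep case-level AUC, the margin and the sample size as they are. Then:

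1. Add to the reader form the side and quadrant of the finding that drives each score, for all four scores (mammography, CESM, abbreviated MRI, full MRI).
2. Code the location of every histologically proven malignant site in the 44 cancer cases.
3. Pre-specify one sensitivity analysis. A cancer case keeps its score only if the recorded location matches any proven malignant site, so that multifocal and bilateral cancers are credited. Otherwise it takes the lowest score.
4. Fix the matching tolerance in advance: same side, and same or adjacent quadrant.
5. Report the location-matched difference with its confidence interval beside the primary result. Giving mismatches the lowest score is a convention, which is why this belongs in a sensitivity analysis.

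Cost: a few seconds for each of 13 x 132 x 4 = 6,864 scores, matching of 13 x 44 x 4 = 2,288 cancer-case scores against coded locations, and one extra analysis. These counts use the 132 cases of section 1.1.4; section 10.1 still says 150.

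If reading is already complete and location was not recorded, state this as a limitation and confine the conclusion to case-level accuracy.

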# 12.2 Sample Size, Accrual Rate and Study Duration

Objective 1: To compare the diagnostic accuracy of CESM with breast MRI for detection of breast cancer.

Area under the ROC curve (AUC) of CESM and MRI will be calculated for each of the 13 readers and compared with Delong & Delong (1988)'s method within each reader. The reader average AUC will be calculated for each modality and the difference between the modalities and its associated 95% confidence interval will be calculated using Obuchowski's method.

Objective 2/3: To compare the diagnostic accuracy of CESM with abbreviated MRI for detection of breast cancer.

Area under the ROC curve (AUC) of CESM and abbreviated MRI will be calculated for each of the 10 readers and compared with Delong & Delong (1988)'s method within each reader. The reader average AUC will be calculated for each modality and the difference between the modalities and its associated 95% confidence interval will be calculated using Obuchowski's method.

Objective 4: Descriptive statistics will be used to evaluate patient responses to the survey

*Sample Size Justification:* The analysis aims to test the non-inferiority of CESM when compared to MRI by establishing no loss of value in the ROC AUC. The null hypothesis is HO: (Reader average AUCCESM- reader average AUCMRI) :S -0.05 versus the alternative HA: (reader average AUCCESM-reader average AUCMRI) > -0.05. The test is based on a 2-sided 95% confidence interval on the difference between the reader average AUCs. The ROC power and the sample size calculations are based on the methods of Zhou, Obuchowski and McClish.

Assuming the average AUC of the two modalities is 0.83, the correlation for same reader, different modalities is 0.47, correlation for different reader, same modality is 0.44, correlation for different reader, different modalities is 0.4 and correlation for group of readers, different modalities is 0.8. The interobserver variability is 0.002 and the intraobserver variability is 0.0004. The pooled readings from 13 readers on 44 cancer cases and 88 non-cancer cases will have at least 80% power to reject the null hypothesis that (AUCCESM - AUCMRI) S -0.05 with a 95% 2 sided confidence interval on the difference. The lower end of the confidence interval for the difference (AUCCESM - AUCMRI) must be greater than -0.05 to accept the alternative hypothesis of non-inferiority.

Accrual Targets for Prospective Recruitment					
Ethnic Category	Sex/Gender				

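### Does naming the benign/malignant call as primary outcome in Section 12.1, on a scale described as 1-5, leave the primary AUC analysis undefined?

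*Combined protocol and SAP*

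**What the plan says.** Section 12.1 (Study Design/Endpoints) describes the rating this way: "Each reader will score each CESM and MRI exam according to the Breast Imaging-Reporting and Data System (BI-RADS), ranging from 1-5". It then states "The primary outcome will be whether the exam is benign or malignant", counting scores 1, 2 and 3 as negative and 4 and 5 as positive, without splitting category 4. After defining positive and negative truth, it closes by saying the team will "compare the BI-RADS score of CESM and MRI with the final outcome of negative or positive truth to determine the area under the curve".

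The reading instructions are finer. Section 1.1.4 says "The radiologist reader will provide a forced BIRADS score of 1,2,3,4a, 4b, 4c, or 5", and Section 10.1 repeats it: "The radiologists will score each case with a BIRADS (Breast Imaging Reporting and Data System) score of 1,2,3,4a, 4b, 4c, or 5". Both attach a separate malignancy probability range to each of 4a, 4b and 4c. Section 1.1.4 also says "We will be evaluating individual and group ROC curves".

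Section 12.2 sets the null and alternative on reader-average AUC for CESM minus that for MRI, with margin -0.05, and adds "The test is based on a 2-sided 95% confidence interval on the difference between the reader average AUCs". It names Obuchowski's method for the interval and DeLong's for comparisons within each reader. Section 12.5 (Analysis of Primary Endpoints) only refers back to 12.1 and 12.2.

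**The concern.** Two things look wrong. First, the quantity called primary in 12.1 is a binary call, while the quantity tested and powered in 12.2 is an AUC. The binary call has no hypothesis, margin, power or sensitivity and specificity analysis. A reader who turns to 12.5 for the answer is sent back to the two sections that differ.

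Second, the AUC is built from a score that 12.1 describes as 1-5 and other sections collect on seven levels. An AUC with ties depends on where the categories are cut. If 4a, 4b and 4c were pooled, and CESM and MRI were called at different specificities, part of the difference compared with -0.05 could come from the pooling. An analyst free to choose five or seven levels after seeing the data could, in principle, affect the non-inferiority conclusion.

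**Working it through.** **1. What is tested.** In 12.2 the null, the alternative, the margin, the interval rule, the method and the power all refer to the reader-average AUC difference. No margin exists for the binary call, so no non-inferiority conclusion could be drawn from it. The tested quantity is unambiguous.

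**2. The plan's own figure.** Section 12.2 claims at least 80% power. Obuchowski's variance, with the stated variabilities taken as variances and a true difference of 0, is

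Var = (2/J){σb²(1-rb) + σw² + σc²[(1-r1) + (J-1)(r2-r3)]}

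with J = 13, σb² = 0.002, rb = 0.8, σw² = 0.0004, r1 = 0.47, r2 = 0.44, r3 = 0.40, and σc² = 0.00199 (binormal approximation, AUC 0.83, 44 cancers, 88 non-cancers). This gives (2/13)(0.0004 + 0.0004 + 0.00199 × 1.01) = 0.000433, SE 0.0208, and power Φ(0.05/0.0208 - 1.96) = 67.1%. Reading the two variabilities as SDs gives 81.1%. The 80% is thus reached on some readings only. The number of rating levels is not an input, so this figure cannot settle the present point.

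**3. Which scale feeds the AUC.** There are three candidates.
- Two levels: the AUC reduces to (sensitivity + specificity)/2, a single operating point. Section 1.1.4 plans ROC curves, so this reading is unlikely.
- Five levels: this needs 4a, 4b and 4c to be merged before the ROC analysis. No section says to do so.
- Seven levels: this is the score as recorded, and it needs no extra step. A scale whose ends are 1 and 5 still ranges from 1 to 5, and category 4 in the cut-point sentence can cover 4a-4c.

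**4. Would the five/seven choice matter?** The documents give no specificities or score distribution, so the inputs here are assumptions: equal-variance binormal model, AUC 0.83 for both modalities, d = √2 × Φ⁻¹(0.83) = 1.349. Let s be specificity at the 3/4 cut. Cuts fall at non-cancer cumulative fractions 0.5s, 0.85s and s, then s + f(1-s) with f = 0.5c/0.97, 0.85c/0.97 and c. Five levels drop the first two values of f. AUC = Σ p1(k)[P0(below k) + p0(k)/2], where p0 and p1 are the category probabilities in non-cancers and cancers. The true difference is zero, so any difference is spurious. Largest absolute values on a 0.05 grid of s, for specificities at most 10 points apart:

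| c | s 0.50-0.80: seven | five | s 0.70-0.95: seven | five |
|---|---|---|---|---|
| 0.80 | 0.0026 | 0.0075 | 0.0071 | 0.0046 |
| 0.85 | 0.0018 | 0.0086 | 0.0074 | 0.0045 |
| 0.90 | 0.0013 | 0.0110 | 0.0075 | 0.0063 |
| 0.95 | 0.0013 | 0.0159 | 0.0075 | 0.0100 |
| 0.97 | 0.0014 | 0.0192 | 0.0074 | 0.0124 |

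In the lower window five levels is always worse, at 15-38% of the 0.05 margin (0.0075/0.05 to 0.0192/0.05). In the higher window the order reverses for c = 0.80, 0.85 and 0.90.

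One wider-gap case, with c = 0.90 and specificities 0.95 and 0.75: seven levels gives 0.8117 - 0.8217 = -0.0100, and five gives 0.8107 - 0.8091 = +0.0016.

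**The case for a change.** The strongest case for a change is that 12.1 is wrong as labelled, the repair is a few words, and the seven-level score is already collected. The scale can also move the estimate by a real part of the margin. With equal specificity in both modalities (0.50-0.80), a true deficit of -0.05 reads -0.047 to -0.051 on seven levels but -0.038 to -0.050 on five, so pooling can shrink a real deficit and favour non-inferiority. An analyst could cite 12.1 for five levels after seeing the data.

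Much of this stands as description. The label is wrong, the number of levels is not written beside the AUC, and the choice of scale is not numerically neutral. What does not stand is the step from there to a plan that misleads. The shift arises only if someone discards subcategories that readers were required to record, without an instruction to do so. The claim that a five-level AUC is the more cut-point dependent is not general either: it holds throughout the 0.50-0.80 window, which has no source in the documents, and fails for part of 0.70-0.95.

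**Conclusion.** No change follows. The primary-outcome sentence in 12.1 is a labelling slip: it sits between the scoring rule and the truth definitions and works as a rule for classifying a read, while 12.2 fixes the tested endpoint in full. The unstated number of levels is a gap that an analyst fills sensibly, because the only BI-RADS score the study collects has seven levels. Following the plan as written gives a sound analysis, and rewording would record what would be done anyway.

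The size of any effect is hypothetical. For specificities at most 10 points apart, the largest spurious difference on the natural seven-level reading is 0.0026 in the lower window and 0.0075 in the higher (5% and 15% of the margin). On the unlikely five-level reading it is 0.0192 and 0.0124. These values rest on an equal-variance binormal model with AUC 0.83 and on assumed cut-points and specificities. The conclusion itself rests on the text: the test is defined in 12.2, seven levels are recorded, and nothing in the plan calls for collapsing them.
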